**Similar Tables:**

Table 14.3.1.2.2 Summary of Study Product Use-Emergent Adverse Events by System Organ Class and MedDRA Preferred Term – Part B

Table 14.3.1.2.3 Summary of Study Product Use-Emergent Adverse Events by System Organ Class and MedDRA Preferred Term – Overall

Table 14.3.1.3.1  
Summary of Serious Study Product Use-Emergent Adverse Events by System Organ Class and MedDRA Preferred Term  
(Safety Population)

System Organ Class MedDRA Preferred Term	Study Product A (N=XX)		Study Product B (N=XX)		Study Product C (N=XX)	
	Subjects [n(%)]	Events [n]	Subjects [n(%)]	Events [n]	Subjects [n(%)]	Events [n]
Any Serious SPUEAE	xx (xx.x)	xx	xx (xx.x)	xx	xx (xx.x)	xx
System Organ Class 1	xx (xx.x)	xx	xx (xx.x)	xx	xx (xx.x)	xx
MedDRA Term 11	xx (xx.x)	xx	xx (xx.x)	xx	xx (xx.x)	xx
MedDRA Term 12	xx (xx.x)	xx	xx (xx.x)	xx	xx (xx.x)	xx
MedDRA Term 13	xx (xx.x)	xx	xx (xx.x)	xx	xx (xx.x)	xx
System Organ Class 2	xx (xx.x)	xx	xx (xx.x)	xx	xx (xx.x)	xx
MedDRA Term 21	xx (xx.x)	xx	xx (xx.x)	xx	xx (xx.x)	xx
MedDRA Term 22	xx (xx.x)	xx	xx (xx.x)	xx	xx (xx.x)	xx
MedDRA Term 23	xx (xx.x)	xx	xx (xx.x)	xx	xx (xx.x)	xx
Etc.	xx (xx.x)	xx	xx (xx.x)	xx	xx (xx.x)	xx

Note(s): For the subject counts, each Study Product Use-Emergent adverse event is counted only once for each subject within each System Organ Class and MedDRA Preferred Term.

Date: VERSION - YYYY-MM-DD

Data Source: XXXX

Program Source: XXXXX.sas

**Similar Tables:**

Table 14.3.1.3.2 Summary of Serious Study Product Use-Emergent Adverse Events by System Organ Class and MedDRA Preferred Term - Part B

Table 14.3.1.3.3 Summary of Serious Study Product Use-Emergent Adverse Events by System Organ Class and MedDRA Preferred Term - Overall

Table 14.3.1.4.1  
Summary of Study Product Use-Emergent Adverse Events by System Organ Class, MedDRA Preferred Term and Severity  
(Safety Population)

System Organ Class MedDRA Preferred Term	Study Product A (N=XX)			Study Product B (N=XX)			Study Product C (N=XX)		
	Mild	Moderate	Severe	Mild	Moderate	Severe	Mild	Moderate	Severe
Any SPUEAE	xx (xx.x)	xx (xx.x)	xx (xx.x)	xx (xx.x)	xx (xx.x)	xx (xx.x)	xx (xx.x)	xx (xx.x)	xx (xx.x)
System Organ Class 1	xx (xx.x)	xx (xx.x)	xx (xx.x)	xx (xx.x)	xx (xx.x)	xx (xx.x)	xx (xx.x)	xx (xx.x)	xx (xx.x)
MedDRA Term 11	xx (xx.x)	xx (xx.x)	xx (xx.x)	xx (xx.x)	xx (xx.x)	xx (xx.x)	xx (xx.x)	xx (xx.x)	xx (xx.x)
MedDRA Term 12	xx (xx.x)	xx (xx.x)	xx (xx.x)	xx (xx.x)	xx (xx.x)	xx (xx.x)	xx (xx.x)	xx (xx.x)	xx (xx.x)
MedDRA Term 13	xx (xx.x)	xx (xx.x)	xx (xx.x)	xx (xx.x)	xx (xx.x)	xx (xx.x)	xx (xx.x)	xx (xx.x)	xx (xx.x)
System Organ Class 2	xx (xx.x)	xx (xx.x)	xx (xx.x)	xx (xx.x)	xx (xx.x)	xx (xx.x)	xx (xx.x)	xx (xx.x)	xx (xx.x)
MedDRA Term 21	xx (xx.x)	xx (xx.x)	xx (xx.x)	xx (xx.x)	xx (xx.x)	xx (xx.x)	xx (xx.x)	xx (xx.x)	xx (xx.x)
MedDRA Term 22	xx (xx.x)	xx (xx.x)	xx (xx.x)	xx (xx.x)	xx (xx.x)	xx (xx.x)	xx (xx.x)	xx (xx.x)	xx (xx.x)
MedDRA Term 23	xx (xx.x)	xx (xx.x)	xx (xx.x)	xx (xx.x)	xx (xx.x)	xx (xx.x)	xx (xx.x)	xx (xx.x)	xx (xx.x)
Etc.	xx (xx.x)	xx (xx.x)	xx (xx.x)	xx (xx.x)	xx (xx.x)	xx (xx.x)	xx (xx.x)	xx (xx.x)	xx (xx.x)

Note(s): For the subject counts, each Study Product Use-Emergent adverse event is counted only once for each subject within each System Organ Class and MedDRA Preferred Term.

Date: VERSION - YYYY-MM-DD

Data Source: XXXX

Program Source: XXXXX.sas

Similar Tables:

Table 14.3.1.4.2 Summary of Study Product Use-Emergent Adverse Events by System Organ Class,  
MedDRA Preferred Term and Severity - Part B

Table 14.3.1.4.3 Summary of Study Product Use-Emergent Adverse Events by System Organ Class,  
MedDRA Preferred Term and Severity - Overall

Table 14.3.1.5.1  
Summary of Study Product Use-Emergent Adverse Events by System Organ Class, MedDRA Preferred Term and Relationship  
(Safety Population)

System Organ Class MedDRA Preferred Term	Study Product A (N=XX)						Etc... (N=XX)					
	Not Related	Unlikely	Possible	Likely	Definitely	Not Related	Unlikely	Possible	Likely	Definitely		
Any SPUEAE	xx (xx.x)	xx (xx.x)	xx (xx.x)	xx (xx.x)	xx (xx.x)	xx (xx.x)	xx (xx.x)	xx (xx.x)	xx (xx.x)	xx (xx.x)		
System Organ Class 1	xx (xx.x)	xx (xx.x)	xx (xx.x)	xx (xx.x)	xx (xx.x)	xx (xx.x)	xx (xx.x)	xx (xx.x)	xx (xx.x)	xx (xx.x)		
MedDRA Term 11	xx (xx.x)	xx (xx.x)	xx (xx.x)	xx (xx.x)	xx (xx.x)	xx (xx.x)	xx (xx.x)	xx (xx.x)	xx (xx.x)	xx (xx.x)		
MedDRA Term 12	xx (xx.x)	xx (xx.x)	xx (xx.x)	xx (xx.x)	xx (xx.x)	xx (xx.x)	xx (xx.x)	xx (xx.x)	xx (xx.x)	xx (xx.x)		
MedDRA Term 13	xx (xx.x)	xx (xx.x)	xx (xx.x)	xx (xx.x)	xx (xx.x)	xx (xx.x)	xx (xx.x)	xx (xx.x)	xx (xx.x)	xx (xx.x)		
System Organ Class 2	xx (xx.x)	xx (xx.x)	xx (xx.x)	xx (xx.x)	xx (xx.x)	xx (xx.x)	xx (xx.x)	xx (xx.x)	xx (xx.x)	xx (xx.x)		
MedDRA Term 21	xx (xx.x)	xx (xx.x)	xx (xx.x)	xx (xx.x)	xx (xx.x)	xx (xx.x)	xx (xx.x)	xx (xx.x)	xx (xx.x)	xx (xx.x)		
MedDRA Term 22	xx (xx.x)	xx (xx.x)	xx (xx.x)	xx (xx.x)	xx (xx.x)	xx (xx.x)	xx (xx.x)	xx (xx.x)	xx (xx.x)	xx (xx.x)		
MedDRA Term 23	xx (xx.x)	xx (xx.x)	xx (xx.x)	xx (xx.x)	xx (xx.x)	xx (xx.x)	xx (xx.x)	xx (xx.x)	xx (xx.x)	xx (xx.x)		
Etc.	xx (xx.x)	xx (xx.x)	xx (xx.x)	xx (xx.x)	xx (xx.x)	xx (xx.x)	xx (xx.x)	xx (xx.x)	xx (xx.x)	xx (xx.x)		

Programming Note: SPUEAE will also be summarized for Study Product B and Study Product C.

Note(s): For the subject counts, each Study Product Use-Emergent adverse event is counted only once for each subject within each System Organ Class and MedDRA Preferred Term.

Date: VERSION - YYYY-MM-DD

Data Source: XXXX

Program Source: XXXXX.sas

Similar Tables:

Table 14.3.1.5.2 Summary of Study Product Use-Emergent Adverse Events by System Organ Class, MedDRA Preferred Term and Relationship - Part B

Table 14.3.1.5.3 Summary of Study Product Use-Emergent Adverse Events by System Organ Class, MedDRA Preferred Term and Relationship - Overall

Table 14.3.2.1  
Listing of Deaths, Other Serious and Significant Adverse Events  
(Safety Population)

Subject Id	Study Part/Day/ Study Product/ Id	SOC MedDRA Preferred Term	Onset Date/Time (Time since Last Dose)	Resolution Date/Time (Duration)	S: Severity R: Relationship to Study Product F: Frequency	O: Outcome S: Serious AE D: AE Lead To Discontinuation	Action Taken With Product Use / Was this AE a result of Study Medication	Was a concomitant treatment given because of the Study Medication the event? / CM #
Xxx	xxxxx xxxxx xx	xxxxxxxxxxxx xxxxxxxxxxxx xxxxxxxxxxxx	YYYY-MM-DD/ HH:MM (DD:HH:MM)	DD/ HH:MM (DD:HH:MM)	YYYY-MM- DD/ HH:MM xxxxxx	xxxxxx	xxxxxx	xxxxxx

Date: VERSION - YYYY-MM-DD

Data Source: XXXX

Program Source: XXXX.sas

Similar Table:

Table 14.3.2.2 Listing of Adverse Events Leading To Study Discontinuation

22ND CENTURY GROUP, INC.  
Project # CEG-P9-153

Algorithme Pharma  
Page 1 of x

Table 14.3.4.1  
Summary of General Biochemistry  
(Safety Population)

Parameter (unit)	Visit	Overall (N=XX)
Lab Test 1		
	Screening      Value	N Mean (SD) Median Min, Max
		xx xx (xx.x) xx.x xx, xx
Etc.	Etc.	

Date: VERSION - YYYY-MM-DD

Data Source: XXXX

Program Source: XXXXX.sas

**Similar Tables:**

Table 14.3.4.2      Summary of Hematology (Safety Population)  
Table 14.3.4.3      Summary of Urinalysis (Safety Population)

Table 14.3.4.4  
Listing of Abnormal On-Study Laboratory Values

Category/ Parameter (Unit)	Reference Range	Subject ID	Visit	Date / Time	Value	Flag	Assessment [1]
----------------------------------	-----------------	------------	-------	-------------	-------	------	----------------

Note: Abnormal values are determined by applying the reference ranges to the results as reported by the external laboratory analysis.

[1] NCS: Not Clinically Significant / CS: Clinically Significant / TBC: To Be Controlled / RPT: Repeated.

Date: VERSION - YYYY-MM-DD

Data Source: XXXX

Program Source: XXXXX.sas

**Similar Table:**

Table 14.3.4.5      Listing of Clinically Significant On-Study Laboratory Values (Safety Population)

Table 14.3.5.1  
Summary of Vital Signs  
(Clinical Safety Set)

Parameter (unit)	Visit		Overall (N=XX)
Vital Sign 1	xx	Value	xx xx (xx.x)
		N	xx
		Mean (SD)	xx.x
		Median	xx, xx
		Min, Max	
	xx	Value	xx xx (xx.x)
		N	xx
		Mean (SD)	xx.x
		Median	xx, xx
		Min, Max	
Etc.	Etc.		

Date: VERSION - YYYY-MM-DD

Data Source: XXXX

Program Source: XXXXX.sas

Table 14.3.5.2  
Listing of Abnormal On-Study Vital Signs Values

---

Parameter (Units)	Subject ID	Visit	Date/Time	Time	Value	MD Safety Review [1]
-------------------	------------	-------	-----------	------	-------	----------------------

---

[1] NCS: Not Clinically Significant / CS: Clinically Significant

Date: VERSION - YYYY-MM-DD Data Source: XXXX

Program Source: XXXXX.sas

**Similar Table:**

Table 14.3.5.3      Listing of Clinically Significant On-Study Vital Signs Values (Safety Population)

22ND CENTURY GROUP, INC.  
Project # CEG-P9-153

Algorithme Pharma  
Page 1 of x

Table 14.3.6.1  
Summary of ECG Parameters  
(Clinical Safety Set)

Parameter (unit)	Visit	Overall (N=XX)		
XXX				
	Screening	Value	N	xx
			Mean (SD)	xx (xx.x)
			Median	xx.x
			Min, Max	xx, xx
Etc.	Etc.			

Date: VERSION - YYYY-MM-DD

Data Source: XXXX

Program Source: XXXXX.sas

22ND CENTURY GROUP, INC.  
Project # CEG-P9-153

Algorithme Pharma  
Page 1 of x

Table 14.3.6.2  
Listing of Abnormal On-Study ECG Assessments  
(Safety Population)

Subject ID	Visit	Date/Time	Position	MD	Safety	Review	Parameter (Unit)	Value
------------	-------	-----------	----------	----	--------	--------	------------------	-------

[1] NCS: Not Clinically Significant / CS: Clinically Significant

Date: VERSION - YYYY-MM-DD

Data Source: XXXX

Program Source: XXXXX.sas

**Similar Table:**

Table 14.3.6.3      Listing of Clinically Significant On-Study ECG Assessments (Safety Population)

SPONSOR NAME  
Project # AAA-P9-999 / SPONSOR PROJECT NUMBER

Algorithme Pharma  
Page 1 of x

Table 14.3.7.1  
Listing of Abnormal On-Study Physical Examination

Body System Examined	Subject ID	Visit	Date/Time	Result (Abnormal Findings)

Date: VERSION - YYYY-MM-DD

Data Source: XXXX

Program Source: XXXXX.sas

**Similar Table:**

Table 14.3.7.2

Listing of Clinically Significant On-Study Physical Examination (Safety Population)

## APPENDIX C

---

### SUMMARY OF PK ANALYSIS

## STATISTICAL ANALYSIS

### Section 14.2.2 Statistical analysis of Plasma Pharmacokinetic Parameters

22ND CENTURY GROUP, INC.  
Project # CEG-P9-153

Algorithme Pharma  
Page 1 of x

Table 14.2.2.1.1  
Pharmacokinetic Statistical Analysis - Product A vs Product B  
(Pharmacokinetic Population)

Parameter	Geometric Lsmeans [1]		P value of Product Effect	Ratio Product A/ Product B	95% Confidence Interval	
	Product A	Product B			Lower Bound	Upper Bound
C max (controlled)	xxxxxx	xxxxxx	xxx	xxx	xxx	xxx
C max (uncontrolled)	xxxxxx	xxxxxx	xxx	xxx	xxx	xxx
AUC (controlled)	xxxxxx	xxxxxx	xxx	xxx	xxx	xxx
AUC (uncontrolled)	xxxxxx	xxxxxx	xxx	xxx	xxx	xxx

[1]: Units are xxx for Cmax, xxx for AUC.

Note(s): An analysis of variance (ANOVA) was performed on the ln-transformed parameters with the following fixed factors: sequence, period, Product, and the following random factor: subject nested-within sequence. The ratio and 95% confidence interval (CI) were obtained by exponentiating the resulting difference in Product least-squares means and its corresponding 95% CI.

Date: VERSION - YYYY-MM-DD

Data Source: XXXX

Program Source: XXXXX.sas

**Similar table(s) :**

T14.2.2.1.2      Pharmacokinetic Statistical Analysis - Product A vs Product C  
T14.2.2.1.3      Pharmacokinetic Statistical Analysis - Product B vs Product C

22ND CENTURY GROUP, INC.  
Project # CEG-P9-153

Algorithme Pharma  
Page 1 of x

Table 14.2.2.2.1  
Between-Product Comparisons of Tmax and T1/2 - Non-Parametric Analysis (First Product Use of Part B)  
(Pharmacokinetic Population)

Pair wise Comparisons	PK Parameter	n	Median of Difference	95% CI	P value
Product A -Product B	xxx	x	XX.X (XX.XX)	XX.X - XX.X	xxxx
Product A -Product C	xxx	x	XX.X (XX.XX)	XX.X - XX.X	xxxx
Product B -Product C	xxx	x	XX.X (XX.XX)	XX.X - XX.X	xxxx

Notes: Median differences between Products and associated 95% CI are estimated using the method of Hodges-Lehmann.

Date: VERSION - YYYY-MM-DD

Data Source: XXXX

Program Source: XXXXX.sas

**Similar table:**

Table 14.2.2.2.2 Between-Product Comparisons of Tmax and T1/2 - Non-Parametric Analysis (Second Product Use of Part B)

## Section 14.2.3.1 Summary of Questionnaires Responses

22ND CENTURY GROUP, INC.  
Project # CEG-P9-153

Algorithme Pharma  
Page 1 of x

Table 14.2.3.1.1  
Use the Product Again - Descriptive Statistics  
(Pharmacodynamic Population)

Visit	Product Use Session	Time Point		Product A (N=XX)	Product B (N=XX)	Product C (N=XX)
xxx	xxxx	xxxx	N	xx	xx	xx
			Mean (SD)	xx (xx.x)	xx (xx.x)	xx (xx.x)
			% CV			
			Min	xx	xx	xx
			Q1			
			Median	xx	xx	xx
			Q3			
			Max	xx	xx	xx
			N	xx	xx	xx
			Mean (SD)	xx (xx.x)	xx (xx.x)	xx (xx.x)
			% CV			
			Min	xx	xx	xx
			Q1			
			Median	xx	xx	xx
			Q3			
			Max	xx	xx	xx
			Etc.			

Date: VERSION - YYYY-MM-DD

Data Source: XXXX

Program Source: XXXXX.sas

22ND CENTURY GROUP, INC.  
Project # CEG-P9-153

Algorithme Pharma  
Page 1 of x

Table 14.2.3.1.2  
Tobacco/Nicotine Withdrawal - Descriptive Statistics  
(Pharmacodynamic Population)

Item	Visit	Product Use Session	Time Point	Value	Product A (N=XX)		Etc. (N=XX)
					N	xx (xx.x)	
xxx	xxx	xxxx	xxxx	Mean (SD)	xx (xx.x)	xx (xx.x)	xx (xx.x)
				% CV			
				Min	xx		xx
				Q1			
				Median	xx		xx
				Q3			
				Max	xx		xx
				Change From Baseline	N	xx	xx
					Mean (SD)	xx (xx.x)	xx (xx.x)
					% CV		
					Min	xx	xx
					Q1		
					Median	xx	xx
					Q3		
					Max	xx	xx
				Etc.			
				Etc.			
				Etc.			

Date: VERSION - YYYY-MM-DD

Data Source: XXXX

Program Source: XXXXX.sas

**Similar table:**

Table 14.2.3.1.3 Direct Effect of Product Questionnaire – Descriptive Statistics

## Section 14.2.3.2 Summary of Subjective Effect Parameters

22ND CENTURY GROUP, INC.  
Project # CEG-P9-153

Algorithme Pharma  
Page 1 of x

Table 14.2.3.2.1  
Summary of Subjective Effect Parameters for Tobacco/Nicotine Withdrawal  
(Pharmacodynamic Population)

Subjective Effect Parameter	Product Use Session		Product A (N=XX)	Product B (N=XX)	Product C (N=XX)	
xxxx	xxx	Value	N Mean (SD) % CV Min Q1 Median Q3 Max	xx xx (xx.x)	xx xx (xx.x)	xx xx (xx.x)
		Etc.				

Date: VERSION - YYYY-MM-DD

Data Source: XXXX

Program Source: XXXXX.sas

**Similar table(s) :**

Table 14.2.3.2.2 Summary of Subjective Effect Parameters for Direct Effect of Product Questionnaire

### Section 14.2.3.3 Statistical Analysis of Subjective Effect Parameters

22ND CENTURY GROUP, INC.  
Project # CEG-P9-153

Algorithme Pharma  
Page 1 of x

Table 14.2.3.3.1.1  
Statistical Analysis of Subjective Effect Parameters for Tobacco/Nicotine Withdrawal – Product A vs Product B  
(Pharmacodynamic Population)

Subjective Effect Parameter	Product Use Session	Lsmeans [1]		95% Confidence Interval		
		Product A	Product B	Difference A – B (SD)	P value of Product Effect	Lower Bound
XXX	Controlled Use	xxxxxx	xxxxxx	xxxxxx (xx.x)	xxx	xxx
	Uncontrolled Use	xxxxxx	xxxxxx	xxxxxx (xx.x)	xxx	xxx

Note(s): The Analysis of Variance (ANOVA) model included the Emax as the response variable, sequence, study product, and period as fixed model effects, baseline score as a covariate and subject nested-within sequence as a random effect.

Date: VERSION – YYYY-MM-DD

Data Source: XXXX

Program Source: XXXXX.sas

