## Statistical Analysis of Subjective Effect Parameters

A linear mixed effects model for analysis of variance/covariance (Proc Mixed) will be performed on  $E_{max\_urge}(\text{controlled})$  and  $E_{max\_plst}(\text{controlled})$ . The model will include  $E_{max}$  as the response variable, sequence, study product, and period as fixed model effects, baseline score as a covariate, and subject nested-within sequence as a random effect. Sequence will be tested using subject nested-within-sequence as the error term. Least square mean (LSM) and 95% confidence interval (CI) for each study product group will be provided. Comparisons will be made for Product A vs. B, A vs. C and B vs. C. The comparison between Product A and Product C will be used as a comparison for internal validity. The LSM difference, p-value and 95% CI of the difference will be provided.

The SAS code for the statistical modeling is:

```
Proc MIXED data=test;
  class subject sequence period product;
  model Emax = sequence period product baseline / ddfm=KR;
  random subject (sequence) / type=UN;
  estimate "Product A vs Product B" product 1 0 -1 /cl alpha=0.05;
  estimate "Product A vs Product C" product 1 0 -1 /cl alpha=0.05;
  estimate "Product B vs Product C" product 0 1 -1 /cl alpha=0.05;
  lsmeans product/cl alpha=0.05;
run;
```

The same model will be used for  $E_{max\_urge}(\text{uncontrolled})$  and  $E_{max\_plst}(\text{uncontrolled})$ , and all  $E_{max}$  of other questions in the Tobacco/Nicotine Withdrawal Questionnaire and Direct Effects of Product Questionnaire for the controlled and uncontrolled product uses in Part B. Baseline (pre-use) score will be included as a covariate for all pharmacodynamics measures for which a pre-use score is collected.

The analysis on  $E_{max\_urge(\text{controlled})}$  and  $E_{max\_plist(\text{controlled})}$  will be based on the pharmacodynamic and the completer populations separately.

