**Similar table(s) :**

T14.2.3.3.1.2	Statistical Analysis of Subjective Effect Parameters for Tobacco/Nicotine Withdrawal - Product A vs Product C
T14.2.3.3.1.3	Statistical Analysis of Subjective Effect Parameters for Tobacco/Nicotine Withdrawal - Product B vs Product C
T14.2.3.3.2.1	Statistical Analysis of Subjective Effect Parameters for Direct Effect of Product Questionnaire - Product A vs Product B
T14.2.3.3.2.2	Statistical Analysis of Subjective Effect Parameters for Direct Effect of Product Questionnaire - Product A vs Product C
T14.2.3.3.2.3	Statistical Analysis of Subjective Effect Parameters for Direct Effect of Product Questionnaire - Product B vs Product C

Table 14.2.3.3.1.4  
Statistical Analysis of Subjective Effect Parameters for Tobacco/Nicotine Withdrawal  
(Completer Population)

Subjective Effect Parameter	Product Use Session	Comparison	Lsmeans [1]			95% Confidence Interval		
			Product	vs Product	Difference (SD)	P value of Product Effect	Lower Bound	Upper Bound
Emax_urge	Controlled Use	Product A vs Product D	xxxxxx	xxxxxx	XXXXXX (xx.x)	xxx	xxx	xxx
		Product B vs Product D	xxxxxx	xxxxxx	XXXXXX (xx.x)	xxx	xxx	xxx
		Product C vs Product D	xxxxxx	xxxxxx	XXXXXX (xx.x)	xxx	xxx	xxx
		Etc.						
Ad libitum	Use	Product A vs Product D	xxxxxx	xxxxxx	XXXXXX (xx.x)	xxx	xxx	xxx
		Etc.						

Note(s): The Analysis of Variance (ANOVA) model included the Emax as the response variable, sequence, study product, and period as fixed model effects, baseline score as a covariate and subject nested-within sequence as a random effect.

Date: VERSION - YYYY-MM-DD

Data Source: XXXX

Program Source: XXXXX.sas

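### The pairwise result shells head the p-value column with the overall product effect, against the pairwise p-value in the methods text, and label the uncertainty of the LS-mean difference as SD

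*SAP*

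**What the plan says.** The SAP section on the statistical analysis of subjective effect parameters plans three pairwise comparisons: "Comparisons will be made for Product A vs. B, A vs. C and B vs. C". For these it states: "The LSM difference, p-value and 95% CI of the difference will be provided". It gives A vs C a named role: "The comparison between Product A and Product C will be used as a comparison for internal validity". Protocol 12.4.3.2 says the same. For PK, Protocol 12.4.4 and the SAP section on PK parameters likewise promise a ratio, CI and p-value for each pair.

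The pharmacodynamic model has product as a single three-level class effect: "model Emax = sequence period product baseline / ddfm=KR". An ESTIMATE statement is then written for each pair.

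The shells in SAP Appendix C read differently:

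- Table 14.2.3.3.1.1 (A vs B, withdrawal questionnaire) heads its p-value column "P value of Product Effect" and its difference column "Difference A – B (SD" (closing bracket omitted here).
- The same shell is reused for the other pairs and for the other questionnaire, including "Statistical Analysis of Subjective Effect Parameters for Tobacco/Nicotine Withdrawal - Product A vs Product C".
- The completer shell (Table 14.2.3.3.1.4) repeats the p-value header and also marks the difference with SD.
- The PK shell (Table 14.2.2.1.1) has the same p-value header and is reused for A vs C and B vs C. It has no SD beside the ratio.
- The pairwise non-parametric shell for Tmax and half-life (Table 14.2.2.2.1) heads its column simply as a p-value, with no mention of a product effect.

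**The concern.** In a model with one three-level product factor, the test of the product effect is a single 2-df F-test. It yields one p-value per endpoint, so A vs B, A vs C and B vs C would all carry the same number. The pairwise p-values come from the ESTIMATE statements instead. A programmer who follows the shell header would take the first; one who follows the methods text would take the second.

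The tables carry both primary endpoints, urge and pleasant under controlled use. Own-brand and gum are expected to differ, since the sample size is built on that difference. An overall test driven by own-brand could therefore sit in the VLN vs gum table beside a VLN vs gum difference near zero.

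The SD label is a separate defect. The uncertainty of a model-based difference is a standard error, and the SAP abbreviation list defines SE separately from SD. A reader of the table could not tell which quantity was printed.

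**Working it through.** **Inputs.** Protocol 12.2 gives two-sided alpha 0.05 and 54 completers. For own-brand vs gum it assumes a difference of 15.85 with SD 28.44 on urge, and 35.21 with SD 31.82 on pleasant (16 completers). It does not say whether each SD is a within-subject SD for one product or the SD of the paired difference, so both readings are carried through.

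**Reproducing the plan's figure.** Paired t-test power by the noncentral t:

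- SD of the difference = √2 × 28.44 = 40.2: minimum n = 53, power 81.1% at 54. For pleasant, minimum n = 15, power 83.3% at 16. Both stated sizes are matched to within one subject.
- SD of the difference = 28.44: minimum n = 28, power 98.0% at 54. This does not reproduce 54.

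The first reading fits the stated sizes better, but the documents do not settle it.

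**Overall product test when VLN equals gum.** Take product means (A, B, C) = (0, δ, 0). Their squared deviations from the mean sum to (2/3)δ². The noncentrality is λ = n × (2/3)δ² / σ², with σ the within-subject SD. The test has 2 and 103 df: 162 observations less 54 for subjects, 2 for period, 2 for product and 1 for the baseline covariate.

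- Urge, σ = 28.44: λ = 54 × (2/3) × 15.85² / 28.44² = 11.2, so P(p<0.05) = 0.848.
- Urge, σ = 28.44/√2 = 20.1: λ = 22.4, so P(p<0.05) = 0.991.
- Pleasant, σ = 31.82: λ = 54 × (2/3) × 35.21² / 31.82² = 44.1, so P(p<0.05) is about 1.00.

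**Simulation check.** 20,000 runs per row of the three-sequence crossover, complete data, no baseline covariate (so 104 error df), A = C:

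| Case | Overall p<0.05 | A–C contrast p<0.05 | Overall significant, A–C not |
|---|---|---|---|
| Urge, within-subject SD 28.44 | 0.847 | 0.051 | 0.797 |
| Urge, SD of paired difference 28.44 | 0.991 | 0.050 | 0.941 |
| Pleasant, within-subject SD 31.82 | 1.00 | 0.048 | 0.952 |

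**SD against SE on urge, n = 54.**

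- Within-subject reading: SE = 28.44 × √(2/54) = 5.47; SD of differences = 28.44 × √2 = 40.2.
- Paired-difference reading: SE = 28.44/√54 = 3.87; SD of differences = 28.4.
- Either way the ratio is √54 = 7.3.

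**The contrast code on which a corrected column depends.** With products ordered A, B, C, the coefficients 1 0 -1 give A − C and 1 -1 0 give A − B. The pharmacodynamic code gives 1 0 -1 to both the A vs B and the A vs C statements. The PK code gives 1 -1 0 to A vs B. As written, the pharmacodynamic A vs B row would carry the A vs C estimate, CI and p-value.

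**The case against.** The strongest reply is that the header is loose wording and not a specified test. No sentence in either document says the column holds the overall three-product test. The methods text and the ESTIMATE statements are pairwise throughout, and no overall product test is planned for reporting. The completer shell gives each comparison its own row and p-value cell, which an overall test would not need. In a table limited to two products, a product effect could mean the effect between those two. SAP section 13 also lets shells be altered slightly without amending the plan. The completer shell still refers to a Product D that does not exist in this study, so it looks like an unedited template.

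Much of that stands. A reader might infer that the SAP has chosen the overall test for VLN vs gum, or that the plan carries an 85% false-positive rate for that comparison. The documents support neither. The 85% arises only if the header is followed against the methods text and VLN truly equals gum. Nor does the SD label play any part in making A vs C look significant.

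What the reply does not remove is the conflict. For a three-level factor, the header is the usual name of the 2-df test, and the SAP's own non-parametric pairwise shell shows the plainer wording was available. The leftover Product D and the miscoded A vs B statement mean that neither the shells nor the code can be presumed checked against the text. The CI in the row would expose a misfilled column, but a primary table whose p-value and CI disagree would itself need correcting.

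**Conclusion.** Wrong as written, in two limited respects. The p-value header in the mixed-model shells conflicts with the pairwise p-value promised in the methods, and the uncertainty label in the pharmacodynamic shells is incorrect. The analysis chosen in the text is pairwise and is not in question.

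The size is conditional. If the column is filled as labelled, VLN equals gum, and own-brand is higher by the planning difference in 54 completers, the A vs C table shows p<0.05 on urge in about 85% of trials (28.44 as a within-subject SD) or 99% (28.44 as the SD of the paired difference). On pleasant it is essentially all trials. The A–C contrast gives 5% in each case. These figures assume normal errors and complete data. The documents use this column in no gatekeeping or decision rule, so the risk is one of misreporting and misreading.

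**What to change.** 1. In Tables 14.2.3.3.1.x, 14.2.3.3.2.x and 14.2.2.1.x, relabel the p-value column as the p-value of that table's (or, in the completer shells, that row's) pairwise 1-df ESTIMATE contrast.
2. In the pharmacodynamic tables, replace SD beside the LS-mean difference with SE.
3. If an overall product test is wanted, show it once per endpoint, in its own row or footnote.
4. At the same time, change the A vs B ESTIMATE in the pharmacodynamic code from 1 0 -1 to 1 -1 0, as in the PK code. Without this, the relabelled column would print the A vs C p-value in the A vs B tables for both primary endpoints.

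The cost is shell edits and one line of code. Design, data collection and sample size are untouched. The change should be made before the tables are programmed.
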